A multidisciplinary EM implementation team developed a LOF assessment tool targeted for the CICU patient population. The assessment tool was created to be easy to use, quantitative, nurse-driven, and potentially generalizable to other CICUs. The creation of the EM team and EM program was an initiative of the Quality of Care Committee in the Division of Cardiology at the Jewish General Hospital.

All patients admitted to the CICU are eligible for the EM program, except for patients meeting pre-defined hemodynamic, respiratory, neurologic, or in-dwelling device criteria. The exclusion criteria were chosen based on expert guidelines for EM safety³¹ and adapted for the acute cardiovascular patient population through collaboration with the multidisciplinary EM team.

For entry into our study, the inclusion criterion is age ≥ 60 years and exclusion criteria are CICU stays less than 24 hours and patients with prehospital LOF 0 (immobile), LOF 1 (bedbound) or 2 (can sit in chair only). Cardiac surgery patients will also be excluded. Patients with a pacemaker or defibrillator will not be included in the bioimpedance substudy (contraindication for use of bioimpedance scale). For the pre-intervention cohort, patients will be prospectively enrolled over a 3-month period by a member of the research team during CICU admission. Following the 3-month pre-intervention period, the intervention (EM program) will be implemented and patients will be prospectively enrolled during CICU admission over a 12-month period by a member of the research team. Informed consent will be obtained for all participants during enrolment by a member of the research team.

Pre-intervention

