Prior to the implementation of the EM intervention, nurses will ascertain and record the prehospital LOF, admission LOF, and LOF on the day of CICU transfer (Appendix A), but will continue usual mobilization practices. Patients who meet eligibility criteria for the EM intervention will be prospectively enrolled over a 3-month period (“pre-intervention cohort”) by a member of the research team during CICU admission. Informed consent will be obtained by a member of the research team. Following discharge, a member of the research team will review the medical record to extract demographic data (age, sex), comorbid illnesses, primary admission diagnosis, frailty status, adverse events during mobilization (falls, dislodgements, and injuries), mobilization activities, length of critical care unit stay, length of hospital stay, mortality, and discharge location.

Intervention

On admission to the CICU, the patient’s treating nurse will assess the patient for the EM program. Patients participating in the EM program will be assessed for enrolment in our study by a member of the research team and will obtain informed consent during CICU admission (“intervention cohort”). The potential participants are likely to be competent and medically fit to be approached for informed consent as patients who are not medically fit will be excluded from the early mobilization program based on clinical factors, which include hemodynamic criteria.

The EM program consists of a progression of functional activities from LOF 0 (lowest mobility) to 5 (highest mobility). Each LOF has 3 primary activities designed to promote the patient to the next level. The nurse will begin with mobility activities based on the LOF that matches the patient’s current status. The nurse and clinical partner will attempt and/or complete each LOF activity once per shift. Physiotherapy assistance is available if required, although not obligatory. Nurses will also provide documentation and education to patients and families on

how to perform and assist with certain activities. LOF, activity attempts/completion, and adverse safety events will be recorded on an EM flowsheet. The intervention will start while the patient is in the CICU and will continue until discharge from the CICU.

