In the patients wearing the accelerometer, data will be recorded on the total time spent in each mobility position, the daily average time spent in each mobility position, the average duration of time for each bout of sitting, standing, and walking, and sleep duration. The step count will also be recorded. The change in skeletal muscle mass from CICU admission to hospital discharge will be recorded.

We will determine which covariates predict improvement in LOF (“responsiveness”) and which ones do not (“non-responsiveness”). We will assess the recovery of physical function at 1 month and 12 months as measured by the SF-36 physical component summary score. We will compare the SF-36 scores of the highest scoring tertile of LOF on hospital discharge with the lowest scoring tertile. We will also compare hospital readmission at 30 days and discharge home vs. healthcare facility.

For safety, we will record the composite and individual components of the number of falls, injuries, and dislodgements over the total number of attempted mobility activities. The results from the intervention cohort will be compared to the pre-intervention cohort for all results.

Data Collection Procedures

Following discharge, a member of the research team will capture the following hospitalization data from the electronic medical record (Chartmaxx, Quest Diagnostics, Madison, New Jersey) for each subject: age, sex, primary admission diagnosis, comorbidities, level of function assessments, CFS score, length of CICU stay, length of hospital stay, discharge location, and referral to cardiac rehabilitation.

Availability of Participants

In the fiscal year 2016-2017, there were 1,356 admissions to the JGH CICU (mean age 68 years old; 477 female (35%)). There were 1,034 patients (76.3%) age ≥ 60 years old. The mean CICU length of stay was 3.3 days and the mean hospital length of stay was 9.5 days. Only one in five patient stays was less than 24 hours in length.

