From the pilot data, we conservatively estimate that about one-third of patients will not be eligible for the study and about 70% will agree to participate. We estimate that the loss of patients to 12 month follow-up will be approximately 10% as the vast majority of CICU patients are followed by hospital-affiliated cardiologists prior to admission or are assigned to one following CICU discharge. Given these estimates, approximately 75 patients are expected to be enrolled and followed during the pre-intervention period and 300 patients are expected to be enrolled and followed during the 12 month intervention period.

Data Analysis

Since the response variable, LOF mobility, is an ordinal variable measured at different timepoints, a cumulative logit model for repeated measurements will be fitted using generalized estimating equations. The model permits us to take into consideration the structure of the correlation between the observations. The model will then be adjusted using covariates of interest, such as age, sex, EM adherence, time spent lying in bed, and illness severity score. Predictors of change in LOF during CICU stay and following hospitalization will be assessed using linear regression. Predictors of EM adherence will also be evaluated using linear regression. All statistical analyses will be performed using SAS version 9.4 by [name], a senior biostatistician affiliated with the Lady Davis Institute Center for Epidemiology.

VII. RESOURCE AVAILABILITY AND SUPPORT

The CICU at the JGH has 16 beds equipped for advanced hemodynamic support and 32 ward beds with telemetry available. Patients are admitted to the CICU mainly for acute primary cardiovascular disease.

The nurse champion's role is to attend EM team meetings, provide education to nursing and clinical partners, and ensure nursing adherence to the protocol. A review of the CICU environment conducted with physiotherapists from the EM team has ensured that the CICU is already equipped with the standard equipment necessary for patient mobilization, particularly for bedbound and immobile patients, and nurses have been trained to use the equipment.

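### The two cohorts are given different entry pools: patients eligible for early mobilization before the intervention, patients participating in it afterwards. One rule should be stated for both periods.

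*Combined protocol and SAP*

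**What the plan says.** Two sentences in section VI (Methods) define who enters the study in each period.

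- Pre-intervention: "Patients who meet eligibility criteria for the EM intervention will be prospectively enrolled over a 3-month period".
- Intervention: the treating nurse first assesses the patient for the EM program on admission to the cardiovascular intensive care unit (CICU). Then: "Patients participating in the EM program will be assessed for enrolment in our study by a member of the research team".

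The study entry criteria stand earlier, under Design, participants and setting, and do not differ by period. Age must be at least 60; "exclusion criteria are CICU stays less than 24 hours and patients with prehospital LOF 0", 1 or 2 (LOF is level of function); cardiac surgery patients are also excluded. Taking part in EM is not among these criteria. The same subsection describes the program as near-universal: "All patients admitted to the CICU are eligible for the EM program, except for patients meeting pre-defined hemodynamic", respiratory, neurologic or device criteria.

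Under Outcome Measures the plan says: "The results from the intervention cohort will be compared to the pre-intervention cohort for all results".

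**The concern.** A pre/post comparison is fair only if the same kind of patient could enter in either period. Eligibility can be judged identically whether or not the program exists. Participation can be observed only once it exists. If participation means that EM was actually begun, the later cohort leaves out eligible patients who were never started, while their counterparts in the earlier period remain in the comparator. Patients whom nurses do not start may differ in ways that also affect LOF, quality of life or length of stay. That difference would be counted as an effect of EM.

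The adjustment under Data Analysis would be only a partial remedy. Of the five covariates named there, age, sex and illness severity could help where selection follows them. EM adherence and time spent lying in bed arise after EM begins and cannot correct for who was started. Prehospital LOF, admission LOF and the Clinical Frailty Scale are collected and could be added, because the covariate list is given as examples.

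**Working it through.** **1. The texts side by side**

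| Item | Pre-intervention | Intervention |
|---|---|---|
| Pool described | Meets EM eligibility criteria | Participating in the EM program |
| Step before study screening | Nurses record LOF; usual mobilization continues | Treating nurse assesses for EM |
| Study entry criteria | Common list | Same list |
| Time point for judging eligibility | Not fixed beyond the CICU admission | Nurse assessment on admission; section IX adds re-screening each shift |

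The pool and the route differ; the study criteria do not. Because patients are re-screened each shift, eligibility can change during a stay, so a common rule also needs a common time point.

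**2. The enrolment forecast**

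Availability of Participants gives 1,034 patients aged 60 or over per year and one in five stays under 24 hours. It also says "we conservatively estimate that about one-third of patients will not be eligible for the study and about 70% will agree to participate", and puts loss to 12-month follow-up at about 10%. The forecast is: "approximately 75 patients are expected to be enrolled and followed during the pre-intervention period and 300 patients are expected" in the 12-month intervention period.

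- Rate per month: 75/3 = 25 and 300/12 = 25.
- Product of the stated inputs: 1,034 × 0.8 × 2/3 × 0.7 × 0.9 = 347 per year, or 347/4 = 87 per quarter.
- Without the 24-hour factor: 1,034 × 2/3 × 0.7 × 0.9 = 434 per year, or 109 per quarter.

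The stated 75 and 300 are not reproduced exactly, but they are described as approximate and conservative. What matters here is the equal rate. A separate participation step would make the later forecast 300 × (1 − p), where p is the share of eligible patients never started. No such factor appears.

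**3. What the literal rule would do**

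Let d be the difference in expected outcome, under usual care, between eligible patients who would be started and those who would not. The mean among starters differs from the mean among all eligible patients by

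p × d.

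This is the spurious pre/post difference before adjustment. It is zero if p = 0 or d = 0, and it takes the sign of d. The documents give neither p nor d, so no size can be stated.

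**4. What the common rule would cost**

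If EM has no effect in patients never started, the by-period effect is (1 − p) times the effect in starters. For assumed values of p: 0% gives 1.0, 10% gives 0.9, and 30% gives 0.7.

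**The case against.** The strongest reply is that one rule is already there in substance.

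- One paragraph sets study entry and then describes both enrolment periods under it.
- The pilot in section V counts 10 of 26 patients as not initially eligible for the study: four for age, two on ventilation, two with transvenous pacemakers and two haemodynamically unstable. EM safety exclusions are thus treated as study exclusions, with no category for not participating.
- The Intervention subsection gives only a clinical reason for being outside the program: "patients who are not medically fit will be excluded from the early mobilization program based on clinical factors".
- EM is nurse-led across the unit, needs no physician order, and has no described opt-in. An eligible patient who receives little of it could be seen as a low-adherence member of the cohort, and adherence is audited and analysed.
- The forecast contains no loss for uptake.

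Most of this stands, and it makes a single intended pool the more likely reading. It does not settle the matter. The pilot reviewed mobility practices before the program was in place, so it shows how eligibility was understood but not whether eligible patients would be started. No sentence equates *participating* with *eligible*. Complete uptake is not assured either: the protocol plans weekly adherence audits with reminders, and section IX lists late recognition of suitable patients and worries about instability and dislodgement as barriers.

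A reader might go further and infer that the later cohort is a favourably selected group, so that the comparison is biased toward EM. The documents do not support this: they give no uptake figure and no information on how non-starters would differ. A reader might also take the gap between 347 and 300 as a hidden uptake loss. It is not specific to the intervention period, since 300/347 and 75/87 are both about 0.86.

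**Conclusion.** The point holds as a defect of wording with a possible effect on the main comparison. The two periods are given different entry pools, and the literal rule lets eligible patients who are never started on EM into one cohort and not the other. The resulting selection is of unknown direction and size, and it is nil if every eligible patient starts or if *participating* simply means screened as eligible. The evidence for one intended pool is good but indirect, so confidence is moderate and the matter ranks as a low-cost improvement.

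A reader might infer from the same passages that the feasibility aim cannot be assessed. That is too strong. Attempts, completion and adherence are recorded. The share of eligible patients who start EM would be a useful addition, but its absence is not the basis of this point.

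**What to change.** In the Intervention subsection, replace the opening of the sentence "Patients participating in the EM program will be assessed for enrolment in our study by a member of the research team" so that it reads: *Patients who meet the EM eligibility criteria and the study entry criteria, assessed at the same time point in the CICU stay in both periods, will be assessed for enrolment whether or not EM is started.* Leave the consent wording and the cohort label as they are; the argument about fitness to consent rests on the clinical exclusions, which still apply. Name the chosen time point in the Pre-intervention subsection too, since neither subsection fixes one for study eligibility.

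Keep the main comparison by period among all enrolled patients. Any analysis restricted to participants should be labelled exploratory and subject to selection, because it sets starters against all eligible controls.

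The textual cost is one clause and one stated time point. The statistical cost is the dilution shown above.

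Optionally, report patients started divided by patients eligible as a feasibility result, from an aggregate count. That means classifying about 1,034/52 = 20 admissions aged 60 or over per week. No passage says that screening results are kept for patients outside EM, and if the task fell to the research assistant, that post is funded for 20 hours per week. A simple tally is therefore preferable to a patient-level log.

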To introduce the EM protocol to the nursing staff, the nurse and physician champion will provide a series of in-service training sessions. Physicians routinely caring for older adults in the CICU and rotating trainees will receive education in the CICU through “Lunch and Learn” conferences. Weekly audits will be performed by the nurse champion to assess for adherence to the EM protocol. Reminders and further education will be provided if necessary. Monthly status reports will be created and disseminated to the nurses and the CICU team.

Frailty will be assessed on admission using the Clinical Frailty Scale (CFS) by the patient’s nurse or a member of the research team (Appendix B).³² The CFS is a simple bedside assessment tool that uses a single global judgement-based measure to assign a score from 1 (very fit) to 9 (terminally ill) with increasing scores from 5 to 8 indicating more advanced frailty.²⁰ The CFS correlates with more comprehensive frailty tools, has been shown to accurately diagnose frailty in critically ill and acute cardiac populations, and provides short and long-term prognostic information.^{20, 21, 33}

Enrolled participants will be approached to participate in this prospective substudy. Patients accepting participation will be asked to wear an accelerometer monitor during CICU stay until the end of hospitalization to capture the time spent in each mobility position. Body composition parameters including skeletal muscle mass and fat mass will be measured daily with a segmental multi-frequency bioimpedance scale.

Instruments

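### Adverse events and mobilization activity come from record review before early mobilization but from a flowsheet during it, so the planned cohort comparison of safety is mixed with a change in recording

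*Combined protocol and SAP*

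**What the plan says.** All references are to section VI (Methods) of the combined protocol and SAP unless stated otherwise.

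- **Pre-intervention, recorded by nurses at the time:** "nurses will ascertain and record the prehospital LOF, admission LOF, and LOF on the day of CICU transfer". Usual mobilization continues. No attempt log or event form is described for this period.
- **Pre-intervention, after discharge:** the research team reviews the medical record, and the items extracted include "adverse events during mobilization (falls, dislodgements, and injuries), mobilization activities".
- **Intervention:** "LOF, activity attempts/completion, and adverse safety events will be recorded on an EM flowsheet". The flowsheet is described for this period only.
- **Intervention, support to staff:** "Weekly audits will be performed by the nurse champion to assess for adherence to the EM protocol". Staff are reminded and retrained where an audit shows the need.
- **Outcome Measures, safety:** the measure is the "number of falls, injuries, and dislodgements over the total number of attempted mobility activities", as a composite and by component. The next sentence reads: "The results from the intervention cohort will be compared to the pre-intervention cohort for all results".

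Data Collection Procedures lists what is taken from the electronic record for every subject. That list names neither adverse events nor mobilization attempts. The plan has no common extraction form for these items, no check of the record review against a second source, and no sensitivity analysis.

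**The concern.** The two cohorts differ in the program they receive and also in how events and activities come to be known. A usual-care activity that was tried but not charted, or a minor dislodgement that nobody wrote up, is lost before EM and has a dedicated line on a form during EM. The safety contrast would then be partly a contrast between two recording methods, and no later analysis of the collected data could separate them.

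Safety is named in hypothesis 1 and in Aim 2, and the closing section on potential impact says the study will supply evidence of safety to support routine use. A reassuring or alarming difference between cohorts would be read in that light.

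**Working it through.** The plan gives no capture rate, event rate or margin for safety, so there is no figure of its own to reproduce on this point. The check is a side-by-side reading followed by algebra.

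**Sources side by side**

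| Item | Pre-intervention | Intervention |
|---|---|---|
| Adverse events | Record review after discharge | EM flowsheet |
| Mobilization | Activities found in the record | Attempts and completion on the EM flowsheet |
| In-unit LOF | Recorded by nurses | Recorded by nurses |

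Both parts of the safety measure change source. The denominator may also change meaning: the pre-intervention list speaks of activities, while the outcome needs attempts. Attempts that were not completed may not be recoverable from routine notes.

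**Bias under no true difference**

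Let each patient in either cohort truly have λ events and m attempts, as the flowsheet would count them. Let record review find a fraction c of the events and d of the attempts.

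- Pre-intervention, observed: cλ events and dm attempts per patient.
- EM, observed: λ events and m attempts per patient.
- Event ratio per patient, EM/pre: λ/(cλ) = 1/c.
- Activity ratio, EM/pre: m/(dm) = 1/d.
- Event ratio per attempt, EM/pre: (λ/m)/(cλ/dm) = d/c.

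The per-patient ratio is 1 only if c = 1. The per-attempt ratio is 1 only if c = d.

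**Hypothetical values** (assumed, not from the documents)

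| c | d | Events per patient, 1/c | Events per attempt, d/c |
|---|---|---|---|
| 0.7 | 0.4 | 1/0.7 = 1.43 | 0.4/0.7 = 0.57 |
| 0.5 | 0.9 | 1/0.5 = 2.0 | 0.9/0.5 = 1.8 |
| 0.5 | 0.5 | 1/0.5 = 2.0 | 0.5/0.5 = 1.0 |

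For c between 0.5 and 0.8, the per-patient ratio runs from 2.0 to 1/0.8 = 1.25.

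**If the flowsheet is itself incomplete.** Suppose it captures 95% of both events and attempts, while record review captures 50–95% of events and 30–95% of attempts. The event-count ratio then runs from 0.95/0.50 = 1.90 down to 0.95/0.95 = 1.00. In the per-attempt ratio the 95% cancels, leaving attempt capture over event capture on record review: from 0.30/0.95 = 0.32 to 0.95/0.50 = 1.90.

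The two kinds of missed record pull in opposite directions. Missed events before EM count against EM; missed attempts before EM count in its favour.

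**Could another measure in the plan serve both periods?** The accelerometer could in principle measure activity the same way throughout. However, it is an optional substudy limited to five monitors at a time, it is not stated to run in both periods, and it does not record adverse events.

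**The case against.** The strongest case on the other side concerns weight and wording. Most of it stands.

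- **The main outcomes are untouched.** Nurses record in-unit LOF in both periods, and the post-discharge LOF, SF-36 and Barthel scores come from the same telephone calls. Length of stay and discharge location are read from the record for every subject. A reader might infer that the effectiveness result is compromised; on this point it is not.
- **Aim 2 can be met within the EM cohort.** Flowsheet counts describe safety and feasibility there without a comparator. The between-cohort safety contrast rests on one general sentence, and the amount of mobilization delivered is not a named outcome. That sentence is nonetheless part of the plan, and it directly follows the safety measure.
- **Better capture during EM is plausible but not documented.** A reader might infer that the flowsheet is complete and verified. The audits concern adherence to the EM protocol, not completeness of recording. The documents do not say how usual mobilization is charted, or that the flowsheet sits outside the medical record. It would therefore be wrong to state as fact that a difference in activity is inflated.
- **Not every rate is necessarily biased.** Per attempt, equal under-capture cancels. This stands, but nothing in the plan would show that capture is equal.
- **Record review does not make the pre-intervention cohort retrospective.** Enrolment is prospective in both periods; only the extraction looks back.
- **Events may be few.** The background describes serious adverse events and catheter dislodgement as rarely reported, and about 75 pre-intervention patients are expected. The contrast may be imprecise whatever the source. That is a second reason for caution and does not remove the first.

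**Conclusion.** The point holds for the between-cohort comparison of adverse events and mobilization activity. The sources differ by cohort, the plan compares them, and nothing elsewhere equalises them. With no true effect, the expected ratio is 1/c per patient and d/c per attempt. The size cannot be stated, because c and d are not in the documents; the values in the tables show only that the per-attempt ratio can fall well below or well above 1.

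A reader might go further and conclude that EM will be made to look safer, or more harmful. The documents support neither. Per attempt, the direction depends on whether record review misses relatively more attempts or more events. Per patient, the ratio exceeds 1 only if record review finds fewer events than the flowsheet, which is likely but undocumented.

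This is a worthwhile low-cost improvement to a safety comparison. It is not a flaw in the primary or listed secondary analyses.

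**What to change.** For the between-cohort comparison of safety and mobilization, extract events and activities in both cohorts with one form, from sources that exist in both periods: nursing notes, incident reports and physician notes. Leave the EM flowsheet out of that comparison. The form should define an event and an activity identically for both cohorts and say whether attempts or only completed activities are counted. Report flowsheet events per attempt only as a within-EM description of safety and feasibility.

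The cost is a change of protocol wording and applying an existing post-discharge record review to the EM cohort for these items. Two downsides should be stated in the protocol. Events noted only on the flowsheet drop out of the comparison. Flowsheet use or EM training may also change routine charting, for example if nurses write fewer narrative notes once a form exists, so common sources remove the formal mismatch without guaranteeing equal capture.

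An optional alternative is to add attempt and event lines to the LOF recording that nurses already do before EM. That would give both periods similar prospective recording, but the prompt could itself disturb usual mobilization practice, which is the control condition. It would have to be settled before the pre-intervention period starts, because attempts not recorded then may not be recoverable.
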